## 2. TRIAL MANAGEMENT

### a. List of Participating Enrolling Clinics or Data Collection Centers

The Medical University of South Carolina (MUSC) Departments of Neuroscience and Psychiatry and Behavioral Sciences will be the recruitment site. There will be two primary recruitment sources:

- **Media:** Advertisements will be placed in local print and online media to aid in recruitment. Media advertisement has been routinely used in other substance abuse studies and has been found to be an effective method of recruiting participants.
- **Database Repository:** [name] laboratory maintains a database repository of subjects that have agreed to be contacted for smoking-related studies. As of 8/1/2015, the repository contains 95 participants that, based upon an assessment within the past 2 years, appear to meet the inclusion exclusion criteria for the current study.

## 3. DATA MANAGEMENT AND ANALYSIS

### a. Data Acquisition and Transmission and Data Entry Methods.

Data will be collected by the appropriate individual (research assistant, Co-PIs, Co-I) using standardized paper and electronic forms and will only be identified with the study's ID of the participant. The codes linking the name of the participant to the study ID will be kept confidential in a secured cabinet by the MPIs. Collected forms will be securely transported to the MPIs' data entry center. Survey completion by participants as well as Research Assistants will enter data in REDCap (Research Electronic Data Capture), a secure, web-based application designed exclusively to support data capture for research studies. REDCap provides: 1) an intuitive interface for data entry (with data validation); 2) audit trails for tracking data manipulation and export procedures; 3) automated export procedures for seamless data downloads to common statistical packages (SPSS, SAS, Stata, R); 4) procedures for importing data from external sources; and 5) advanced features,

such as branching logic and calculated fields. These procedures are effective in minimizing data entry errors (e.g., missing or errant data). The data analysis plan is outlined in Section D.

**b. Quality Assurance.** Accuracy and completeness of the data collected will be ensured by weekly review. A 10% random sample of the primary source document will be crosschecked with the database as part of the targeted DSMB audit. If inaccuracies exceed 4%, then a second 10% will be randomly chosen for audit. The REDCap system does not accept outliers, illogical response patterns, etc. The Co-PIs will have weekly meetings with the research assistants to discuss qualitative comments received during data collection and any problems in data collection or entry. The statistician will periodically examine the database to look for irregularities. Initial data analyses will examine distributions of variable scores and comparability of baseline characteristics across conditions in case analyses need to be adjusted for these. Confidentiality protections are outlined above.

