While in the MRI scanner for their baseline session, fMRI-1, participants will lie still while undergoing a high resolution anatomical scan, as well as perform the CR task. Participants will be inside of the MRI scanner for approximately one hour. After the scanning portion of the visit, participants will perform the SRRT and smoke a cigarette through the CReSS smoking topography system.

**Cue Reactivity Task (CRT).** Participants will be scanned while performing a smoking CR task that involves viewing cigarette smoking-related images (e.g. cigarette) and non-smoking control images (e.g. pencil) over the course of ~8 ½ minutes [5, 7-13]. Participants will be asked to periodically report their level of craving in response to the images.

**Smoking Regulation Relapse analog task (SRRT: Fig. 2.** The SRRT was developed by the PI ([name]), and currently in use in his laboratory to assess relations between success in regulating mood and craving and subsequent smoking self-administration. The task is comprised of two phases. The first phase—similar to [6]—presents smoking or neutral images and instructs participants to either react to how the stimulus would make you feel Now (e.g. immediate satisfaction) or reframe the content into how it would make you feel Later (e.g. the deleterious health effects of smoking). Following each trial, self-reported craving ratings are collected. This is shown to be an effective probe of craving regulation that is mediated by corticostriatal function [6]. The task randomly presents 24 trials of neutral (n=12) and smoking (n=12) images, half of each divided into instruction with Now or Later, over a 6-min block. Participants have the choice to earn \$1 for each subsequent block up to 60 min., or quit the task and smoke a cigarette using a pocket CReSS system and topography measures recorded (e.g. # puffs, puff volume, IPI). In order to verify smoking topography measures, participants will be video recorded during while smoking through the CReSS device. Preliminary findings from a mood-regulation variant of the SRRT developed by

[figure not shown]

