#### *Data Analysis.*

**fMRI data preprocessing.** fMRI data will be preprocessed using SPM8 to remove noise and artifacts, correct for slice acquisition time, motion corrected [14], temporally realigned using B-spline interpolation, normalized into standard stereotaxic space (MNI) with an isotropic 2mm voxel size and smoothed with an 8mm FWHM Gaussian filter. **Voxel-wise, within-mask analysis.** At the 1st-level, data will be analyzed using the GLM [15]. Each of 2 blocks of interest (Drug, Control) will be modeled as a boxcar canonically convolved hemodynamic response function, and in scanner heart-rate, respiration rate and motion parameters will be entered as nuisance covariates. Next, Drug-Control contrast images will be generated, entered into a 2nd-level, 2 (VRN: Yes, No) x 2 (NAC: Yes,

*Figure 3. ROI:* superior, middle, & inferior frontal gyri (SFG, MFG, IFG), dorso- & ventro-medial, ventrolateral and prefrontal cortex (dmPFC, vIPFC, vMPFC), anterior cingulate cortex (ACC), insula, amygdala, putamen, nucleus accumbens (NA), caudate & thalamus.

No) ANOVA, and analyzed within an ROI mask (Fig. 3),  $p < .05$ , corrected for multiple comparisons. fMRI data analysis plan: Resting-state functional connectivity will be assessed using the conn13 SPM8 toolbox. First, experimental design variables, pre-processed functional images filtered with a 0.01 to 0.08 Hz band-pass filter and normalized (modulated to preserve volume) T1 and segmented images will be uploaded into the toolbox. 5-mm spheres will be created around MNI coordinates for *a priori* regions of interest (ROIs) that include: bilateral amygdala, nucleus accumbens, dACC and inferior, middle and superior frontal gyri. The conn13 toolbox uses PCA to isolate potentially confounding noise from nuisance covariates using default settings. Individuals' WM and CSF templates, in-scanner heart-rate (HR), respiration rate and movement parameters will be included as covariates. Connectivity matrix for the nucleus accumbens and amygdala seeds will each be entered into separate: 2 (NAC: Yes, No) x 2 (VRN: Yes, No) ANOVAs. We will follow-up with exploratory whole brain analyses.

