**d. Power Calculation and Sample Size**

Our primary aim is to evaluate the effects of VRN+NAC on fMRI BOLD signal. We have investigated multiple components of these effects in previous studies: Effects of smoking on cue-reactivity: In a previous study, smoking abstinence increased activation in dlPFC to visual cues in smokers with low negative affect ( $d = .65$ ); the opposite pattern was observed among smokers with elevated negative affect ( $d = -1$ ) which resulted in a significant smoking state by negative affect group interaction ( $d = 1.5$ ). Effects of smoking abstinence on resting-state functional connectivity: Smoking abstinence strengthened rsFC in an amygdala-striatal circuit ( $rZ$ 's between .56 and .91) and weakened rsFC in the corticostriatal network ( $rZ = .71$ ). Effects of NAC on rsFC: In our ongoing PBO-controlled NAC fMRI pilot study (N=20), we find that as compared to the PBO group, smokers in the NAC group exhibit stronger rsFC in the

corticostriatal network ( $r_s = .79$ ). Whereas we have not specifically assessed the interactive effects of NAC +VRN on brain function, the studies listed above provide strong support that we will observe significant effects in a sample of 100 participants. The effects of NAC+VRN on neural network function (Aim 1) and brain CR (Aim 2) will be assessed. If we assume that as with our studies of smoking abstinence and NAC, these effects are of medium to large size (e.g.  $d = .8$ ), with alpha =.05 (1-tailed), a sample of 25 participants in each treatment group will result in power  $>.90$  for detecting effects of treatment on rsFC and CR-BOLD response. In sum, we are confident that the proposed sample size of 100 will be sufficient to test Aims 1a and 2a.

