## 9. APPENDIX

List of questionnaires to be used during the study. Questionnaires / Task	Measure
CAARS-SR	ADHS
MINI	intake
PANAS	Affect [State]
TAS-20	Alexithymia
BAI	Anxiety
Caff - 24hrs	behaviors
Log/Diary Review	behaviors
BDI-II	Depression
CES-D	Depression
DTS	Distress Tolerance
CERQ	Emotion regulation
ERQ	Emotional Regulation
UPPS-P	Impulsivity
Basic Demo	intake
Employment Hx	intake
Family Smoking History	intake
30 day TLFB ETOH/drug	intake/behaviors
30 TLFB cigs/other tobacco	intake/behaviors/elig
FFMQ	Mindfulness
CQ	Nicotine
FTND	Nicotine
mCEQ	Nicotine
NWSC	Nicotine
QSU-B	Nicotine
Craving/Temptation to Smoke	Nicotine
Readiness/Confidence to Quit	Nicotine
Smoking Hx Form	Nicotine
Smoking Occasion	Nicotine
WI-PREPARE	Nicotine
WISDM-68	Nicotine
SHAPS	Reward processing/Anhedonia
MRI Screening Form	safety
Penetration of the Blind	Randomization

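### Baseline adjustment depends on how balanced the randomised arms turn out, and no covariate is fixed in advance, so precision available from data already collected may be lost

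*Combined protocol and SAP*

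**What the plan says.** Section 3b (Quality Assurance) says that the first data analyses will look at score distributions and at "comparability of baseline characteristics across conditions in case analyses need to be adjusted for these". It names no covariate, no criterion for deciding that adjustment is needed, and no adjusted model. Section 3a sends the reader to Section D for the analysis plan, but Section D is Protection of Human Subjects. The analysis text is in Section C.

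In Section C, Data Analysis, the cue-reactivity "Drug-Control contrast images will be generated, entered into a 2nd-level" two-by-two (VRN by NAC) ANOVA. The connectivity matrices for the two seed regions "will each be entered into separate: 2 (NAC: Yes, No) x 2 (VRN: Yes, No) ANOVAs". The covariates named there are image-noise terms: motion, heart rate and respiration for the cue task, and for connectivity the WM and CSF templates and heart rate, while "respiration rate and movement parameters will be included as covariates". None is a baseline characteristic of the participant.

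Baseline data exist. At the Day 0 scan participants have an anatomical scan "as well as perform the CR task", and the first dose is on the morning of Day 1. The appendix ("List of questionnaires to be used during the study") includes the FTND and a 30-day timeline follow-back for cigarettes.

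**The concern.** When arms are randomised, any baseline difference between them is chance. A covariate earns its place by predicting the outcome, and observed imbalance is a poor guide to that. If observed comparability is the only ground for adjusting, a strong predictor that happens to be balanced stays out of the model, and its share of the residual variance stays in the standard error.

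The wording also leaves the choice of adjusted model to someone who has already compared the arms. Nothing says that the choice is made before outcomes are seen. What is at stake is precision and a fixed analysis, mainly for arm-versus-arm contrasts with about 25 per group.

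**Working it through.** **Inputs from the plan** (section 1d, Power Calculation and Sample Size): d = .8, alpha .05 one-tailed, four arms of 25. The plan states that "a sample of 25 participants in each treatment group will result in power" above .90. **Assumed, because the documents give no figure:** covariate-outcome correlation ρ of .3, .5 or .7, and an imbalance trigger at p<.05, .10 or .20.

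**1. The plan's power.** For 25 v 25 by the normal approximation: Φ(.8 × √(25/2) − 1.645) = Φ(2.828 − 1.645) = Φ(1.183) = .882. By the t distribution it is .874 (48 df) or .878 (96 df). For a factorial main effect, 50 v 50: Φ(.8 × √25 − 1.645) = Φ(2.355) = .99. The stated figure is met for main effects and narrowly missed for a pairwise contrast.

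**2. What a fixed covariate gives.** Residual variance is multiplied by (1 − ρ²), which equals a sample of 25/(1 − ρ²) per arm.
- ρ = .3: factor .91, equal to 27.5 per arm
- ρ = .5: factor .75, equal to 33.3 per arm
- ρ = .7: factor .51, equal to 49 per arm

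The normal approximation Φ(2.828/√(1 − ρ²) − 1.645) gives .91, .95 and .99. Simulation gives about .90, .94 and .99.

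**3. What imbalance-triggered adjustment gives up.** The variance that a covariate can remove comes from its chance imbalance. If adjustment happens only when a k-df imbalance statistic exceeds its critical value c, the share of the variance reduction lost is P(χ² on k+2 df < c). Here k = 1 for a pairwise balance test and k = 3 for a four-arm test.

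| Trigger | Pairwise test | Four-arm test |
|---|---|---|
| p<.05 | 72% | 83% |
| p<.10 | 56% | 72% |
| p<.20 | 35% | 54% |

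**4. Power for 25 v 25, d = .8, one-sided, trigger p<.05** (simulation, 100,000 trials per setting):

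| ρ | Balance test | Unadjusted | Triggered | Fixed | Share of power gain lost |
|---|---|---|---|---|---|
| .3 | pairwise | .878 | .881 | .901 | 86% |
| .3 | four-arm | .878 | .879 | .900 | 93% |
| .5 | pairwise | .879 | .888 | .943 | 86% |
| .5 | four-arm | .877 | .883 | .943 | 92% |
| .7 | pairwise | .878 | .895 | .989 | 84% |
| .7 | four-arm | .878 | .889 | .989 | 90% |

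With a p<.20 trigger, 56% to 73% of the power gain is still lost.

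**5. Type I error.** With one covariate and a p<.05 trigger, one-sided size is .042 to .048. With a p<.20 trigger and ρ = .7 it falls to .032. The procedure is conservative.

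**The case against.** The strongest reply is that section 3b sets no rule. It sits under Quality Assurance and states no significance test, threshold or automatic trigger. The unadjusted ANOVA in Section C is the default. This stands: the p<.05 trigger above illustrates one way of applying the sentence and is not the plan's procedure. It does not remove the point. The unadjusted default forgoes the whole gain, and observed comparability is the only ground offered for departing from it.

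A reader might infer that the false-positive rate is inflated. The documents do not support that. Selecting on baseline balance gives a slightly conservative test. A rate of about .09 appears only if the smallest p-value is taken from the unadjusted model and ten one-covariate models, and the plan describes no such practice.

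A reader might also infer from the 33 appendix entries that some imbalance is bound to trigger adjustment. For 20 independent variables the chance of at least one p<.05 is 1 − .95²⁰ = .64. But the list has no visit column, includes items that are not scales, and nothing says that all would be compared.

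Finally, at the plan's own d = .8 the main effects already have about .99 power, so adjustment can add about one point there. This stands and limits the point to pairwise contrasts and to effects smaller than planned.

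**Conclusion.** The point holds in a limited form. Adjustment depends on chance balance, no baseline covariate is fixed, and the adjusted model is left open after data are seen. If the trigger were p<.05 or p<.10, most of a fixed covariate's benefit would be lost, in variance and in power. At p<.20 most of the power gain is still lost, but only 35% of the variance reduction with a pairwise test.

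The absolute size depends on ρ, which the documents do not give. For a 25 v 25 contrast at d = .8 the difference between fixed and triggered adjustment is about 2 power points at ρ = .3, about 6 at ρ = .5 and 9 to 10 at ρ = .7.

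It would be tempting to claim the larger gains for demographics or smoking history, but nothing in the documents supports correlations of .5 to .7 between those and BOLD signal or connectivity. Day 0 cue reactivity is the strongest candidate for Aim 2 because it is the same measure taken before the first dose. Its correlation with Day 10 is also unknown, since the Day 10 scan follows three days of abstinence.

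This is a loss of precision and of prespecification. It does not invalidate the planned tests.

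**What to change.** Replace the adjustment clause in section 3b with a short covariate list, fixed before unblinding and used whatever the observed balance:
- Aim 2 cue-reactivity analysis: Day 0 cue reactivity. State the form in which it enters the second-level model.
- Other VRN by NAC comparisons: one baseline dependence or consumption measure (FTND, or cigarettes per day from the timeline follow-back).

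Report baseline characteristics by arm descriptively, and label any adjustment prompted by imbalance a sensitivity analysis. Correct the reference to Section D so that it points to the analysis text.

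The Day 0 session description lists no resting-state run, so a baseline connectivity covariate for Aim 1 may not exist. If such a run is acquired, say so and consider it.

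The cost is a paragraph of wording and one degree of freedom per covariate out of 96 (100 participants less four arm means). The Day 0 scan covariate also needs a stated rule for participants without a usable baseline scan, whether exclusion or another handling. No new data are needed.

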#### **4. Regulatory Issues.**

##### **a. Reporting of SAEs**

Serious adverse events (SAEs) are defined as events, related or unrelated, that require or prolong hospitalization or result in congenital defects, death, disability, or life threatening event. The Institutional Review Board (IRB) of the Medical University of South Carolina (MUSC) will be immediately informed orally of an SAE as soon as the investigator, co-investigators, or study staff are made aware of it. This information will be communicated orally and by fax immediately to the IRB. A written report will be filed within 72 hours to the IRB, the NIDA Project Officer, and (when applicable) to the FDA. As further clinical information is obtained, follow-up and final SAE reports will be filed with the IRB, NIDA, and the FDA (when appropriate).

##### **b. Reporting of IRB Actions to NIDA**

The initial IRB approval will be forwarded to NIDA for review. The protocol will be reviewed annually by the IRB, and annual renewals will be forwarded to NIDA.

##### **c. Report of Changes or Amendments to the Protocol**

All proposed changes/amendments to the protocol will be discussed with the NIDA Project Officer prior to implementation. Amendments will then be filed with the IRB. IRB approval of such amendments will be forwarded to the NIDA project officer, and the original amendment approvals will be filed in the primary document manual.

##### **d. Trial Stopping Rules**

There are no plans for interim analysis of efficacy data. However, this issue will be discussed further with NIDA and our Project Officer in the event such a formal interim analysis of efficacy is desired. If so, a formal blinded interim analysis of efficacy would be done halfway through the trial to determine if the findings are so efficacious for a particular group that it would be necessary to consider terminating the trial early. In any event, should such an analysis be undertaken, the statistical guidelines, which would be utilized, would indeed be "guidelines" rather than formal rules. It is expected that the DSMB would deliberate, noting in particular whether boundaries had been crossed that would suggest that it would be statistically appropriate terminate the trial. If in fact such a formal interim efficacy analysis is undertaken, it will be utilizing the O'Brien-Fleming (OF) alpha spending function (O'Brien PC & Fleming TR,

1979, "A Multiple Testing Procedure for Clinical Trials," *Biometrics*, Volume 35, pages 549-556). The O'Brien-Fleming boundaries would result in an extremely conservative comparison midway through the trial, making it quite difficult to cross a boundary. The advantage of this criterion is that the final analysis is still preserved very closely to the planned 0.05 significance level. This analysis as noted would be done midway through the trial, in particular when approximately one-half of the total sample size has been enrolled and followed.

In addition to the formal analysis for efficacy, safety data will be examined on an ongoing basis by the DSMB. These data will be provided to the DSMB at whatever level of detail they request. Comparisons suggested by the DSMB will be performed in order to make comparisons between treatment groups. Adverse experiences and safety contrasts will be performed as requested by the DSMB when 25%, 50%, 75%, and 100% of the sample is enrolled and followed. DSMB reports will be included as part of each scheduled report to NIDA.

**e. Disclosure of Any Conflict of Interest in the DSM**

The Principal Investigators, Co-Investigators, and members of the Data and Safety Monitoring Board (DSMB) will report on an annual basis, or more frequently when needed, any conflicts of interest or apparent conflicts of interest to the NIDA Project Officer. On an annual basis, the above individuals will sign a disclosure statement. It should be noted that on an annual basis the investigator fills out a disclosure/conflict of interest questionnaire that is reported and reviewed by the IRB, and when necessary by the university-wide Conflict of Interest Committee.

**f. Clinical Trials Registration**

Prior to the start of the study, the protocol will be registered on the clinical trials registry ([www.clinicaltrials.gov](http://www.clinicaltrials.gov)). All serious adverse events will be reported to the MUSC Institutional Review Board (IRB) within 24 hrs. Follow-up of all serious adverse events will be reported as well. All adverse events are reviewed weekly by the Co-PIs and yearly by both the DSMB and the IRB. Any significant actions taken by the local IRB, including significant protocol changes, will be relayed to NIDA. We anticipate the serious adverse event rate to be extremely low. If monitoring indicates otherwise, we will convene a special meeting of the DSMB.

## **5. TRIAL SAFETY**

**a. Potential Risks and Benefits for Participants**

Potential risks incurred by participants include adverse events related to study medication.

Varenicline: The Varenicline package insert ([http://www.pfizer.com/files/products/uspi\\_chantix.pdf](http://www.pfizer.com/files/products/uspi_chantix.pdf)) details adverse events associated with the medication. Specifically, it reports that "the most common adverse reactions (>5% and twice the rate seen in placebo-treated patients) were nausea, abnormal (e.g., vivid, unusual, or strange) dreams, constipation, flatulence, and vomiting."

Meta-analyses of the four main adverse events in varenicline versus placebo groups in adult trials yielded relative risks (RRs) of 3.21 (95% CI 2.71, 3.80) for nausea, 1.50 (95% CI 1.26, 1.79) for insomnia, 2.79 (95% CI 2.09, 3.72) for abnormal dreams, and 1.20 (95% CI 1.00, 1.45) for headache (Cahill et al., 2009).

While post-marketing anecdotal reports of psychiatric adverse events led to an FDA “black box” warning for varenicline, a meta-analysis of controlled varenicline trials in adults (total n=3091 randomized to varenicline) yielded no significant increase, relative to placebo, in any psychiatric adverse events aside from sleep disturbance (Tonstad et al., 2010). Additionally, a “real world” primary care cohort study including 10,973 smokers prescribed varenicline revealed no evidence of increased risk of self-harm, compared with smokers prescribed other cessation pharmacotherapies (Gunnell et al., 2009).

